8.3 Visit 3/Day 21 (Final Visit)

Changes in concomitant medication or non-drug treatments/procedures will be documented in the CRF.

Spontaneous reporting of AE's, AE's captured in the subject diary card, and those elicited by asking subjects to respond to a non-leading question such as "How do you feel?" will be assessed and any AEs recorded in the CRF.

8.3.1 Dermatologist Assessment

A final assessment by the same dermatologist, where possible, will be completed at the end of the 21 (+2) day product use period (Visit 3).

The intensity of any visual signs of dermal irritation will be recorded according to the grade of the reactions according to the Dermatological Evaluation ([Dermatologist Assessment of Signs and Symptoms of Cutaneous Irritation](#)).

The dermatologist is responsible for grading the level of cutaneous irritation and their opinion on the correct classification of the irritation scores is final.

Any observed cutaneous response that can be denoted according to the grade of the reactions will not be considered an adverse event. Only in the case of unusual reactions, in the opinion of the qualified dermatologist, will these reactions and the consequences observed upon evaluation be documented as AE's.

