5.8 Clinical Assessor Qualifications

Where ever possible all clinical assessments will be made by a single qualified dermatologist and a single qualified ophthalmologist for all subjects throughout the study. Each assessor will visually evaluate subjects for eligibility to enter and continue in the trial at the start (Visit 1 or Visit 2 if not combined) and at the end of the 21 (+2) day product use period (Visit 3).

The intensity of any visual signs of dermal irritation will be recorded according to the grade of the reactions in the Dermatological Evaluation ([Safety and Other Assessments](#)). The dermatologist is responsible for grading the level of cutaneous irritation and their opinion on the correct classification of the irritation scores is final. Every effort will be made to ensure the same dermatologist will be used to evaluate all subjects in the study.

The intensity of any visual signs of ocular irritation will be recorded according to the grade of the reactions in the Ophthalmological Evaluation ([Safety and Other Assessments](#)). The ophthalmologist is responsible for grading the reactions, their opinion on the classification of the ocular irritation scores is final. Every effort will be made to ensure the same ophthalmologist will be used to evaluate all subjects in the study.

Any observed cutaneous or ocular response that can be completely described by the dermatologist or ophthalmologist grading scales will not be considered an adverse event. Only in the case of unusual reactions, in the opinion of the clinical expert, will these reactions and the consequences observed upon evaluation be documented as AEs.

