8.2.3 Dermatologist Assessment

A qualified dermatologist will visually assess the subject at Visit 2 (baseline) prior to randomization to determine subject's eligibility to continue in the study. This will ensure the subject is free of any preexisting dermatological pathology prior to using the study products (Edward and Norman, 1982).

Subjects will only be considered eligible to enter the study if they have a dermatologist signs and symptoms cutaneous irritation score of 0.5 (very slight) or greater for erythema and dryness and a score of 0 (none) or 0.5 (very slight) for scaling and edema, as this is representative of the target consumer for the finished product. Subjects presenting with a score of 1 (slight) or greater for edema are excluded from the study as this condition is not reflective of the target population.

Any subject with a score of 3 (severe) in any attribute will exclude the subject from the study, as this condition is not reflective of the target population for the product.

The intensity of any visual signs of dermal irritation will be recorded according to the grade of the reactions per the Dermatological Evaluation ([Safety and Other Assessments](#)). The dermatologist is responsible for grading the level of cutaneous irritation and their opinion on the correct classification of the irritation scores is final. Scores will be directly entered into the CRF.

Any observed cutaneous response that can be denoted according to the grade of the reactions will not be considered an adverse event. Only in the case of unusual reactions will these reactions and the consequences observed upon evaluation be documented as AE's.

If Visit 2 is combined with Visit 1, the initial (baseline) dermatologist assessment will be conducted prior to the LAST procedure. Randomization and initial test product application will occur at least 30 minutes after the LAST procedure.

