8.3.2 Ophthalmologist Assessment

A final assessment by the same ophthalmologist, where possible, will be completed at the end of the 21 (+2) day product use period (Visit 3).

The intensity of any visual signs of ocular irritation will be recorded according to the grade of the reactions according to the Ophthalmological Evaluation ([Ophthalmologist Assessment of Signs and Symptoms of Ocular Irritation](#)).

The ophthalmologist is responsible for grading the reactions, their opinion on the classification of the ocular irritation scores is final.

Any observed ocular response that can be denoted according to the grade of the reactions will not be considered an adverse event. Only in the case of unusual reactions, in the opinion of

the qualified ophthalmologist, will these reactions and the consequences observed upon evaluation be documented as AE's.

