- Anticipated day-to-day fluctuations of pre-existing disease(s) or condition(s) present or detected at the start of the study that do not worsen.
- Any observed response to the LAST that can be denoted according to the score of the reactions (per [Table 8-1 Lactic Acid Sting Test Score](#)) will not be considered an adverse event. Only in the case of unusual reactions, in the opinion of the qualified dermatologist, will these reactions and the consequences observed upon evaluation be documented as AE's.
- Any observed cutaneous or ocular response that can be denoted according to the grade of the reactions (per [Safety and Other Assessments](#)) will not be considered an adverse event. Only in the case of unusual reactions, in the opinion of the clinical expert, will these reactions and the consequences observed upon evaluation be documented as AEs.

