10.2 Definition of a Serious Adverse Event (SAE)

A Serious Adverse Event (SAE) is a particular category of an adverse event where the adverse outcome is serious. If an event is not an AE per definition above, then it cannot be an SAE even if serious conditions are met (e.g. hospitalization for signs/symptoms of the disease under study, death due to progression of disease).

A serious adverse event is any untoward medical occurrence at any dose that:

- **Results in death**
- **Is life-threatening**
 - The term 'life-threatening' in the definition of 'serious' refers to an event in which the subject was at risk of death at the time of the event. It does not refer to an event, which hypothetically might have caused death, if it were more severe;
- **Requires inpatient hospitalization or prolongation of existing hospitalization**
 - In general, hospitalization signifies that the subject has been detained (usually involving at least an overnight stay) at the hospital or emergency ward for observation and/or treatment that would not have been appropriate in the physician's office or outpatient setting. Complications that occur during hospitalization are AEs. If a complication prolongs hospitalization or fulfills any other serious criteria, the event is serious. When in doubt as to whether "hospitalization" occurred, or was necessary, the AE should be considered serious.
 - Hospitalization for elective treatment of a pre-existing condition that did not worsen from baseline is not considered an AE.
- **Results in persistent or significant disability/incapacity**
 - The term disability means a substantial disruption of a person's ability to conduct normal life functions.
 - This definition is not intended to include experiences of relatively minor medical significance such as uncomplicated headache, nausea, vomiting, diarrhea, influenza, and accidental trauma (e.g. sprained ankle) which may interfere with or prevent everyday life functions but do not constitute a substantial disruption
- **Results in congenital anomaly/birth defect**
- **Other situations:**

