10.3 Time Period and Frequency for Collecting AE and SAE Information

All AEs, and therefore all SAEs will be collected immediately after a subject provides consent to participate in the study by the completion (signature) of the ICF and until 5 days following last administration of the study product (or last procedure).

Medical occurrences that began before obtaining informed consent will be recorded in the Medical History/Current Medical Conditions section of the CRF not the AE section.

Details recorded by the subject on a diary or similar document that meet the definition of an AE must also be discussed with the subjects and transcribed in the AE section of the CRF.

All SAEs will be recorded and reported to the sponsor or designee immediately and under no circumstance should this exceed 24 hours. The investigator will submit any updated SAE data to the sponsor within 24 hours of it being available.

Investigators are not obligated to actively seek AEs or SAEs after the conclusion of the study participation. However, if the investigator learns of any SAE, including a death, at any time after a subject has been discharged from the study, and he/she considers the event to be reasonably related to the study product or study participation, the investigator must promptly notify the sponsor.

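### As written, a gradable skin or eye reaction not judged 'unusual' is not an AE, so it cannot be an SAE even when it meets a seriousness criterion

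*Protocol*

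**What the plan says.** Protocol 10.1 lists among the events that are not AEs "Any observed cutaneous or ocular response that can be denoted according to the grade of the reactions", with a cross-reference to Safety and Other Assessments (9.2). Protocol 8.3.1 repeats the rule for the final dermatologist visit ("Any observed cutaneous response that can be denoted according to the grade of the reactions will not be considered an adverse event") and 8.3.2 does so for the eye ("Any observed ocular response that can be denoted according to the grade of the reactions will not be considered an adverse event"). Section 5.8 uses a stricter test, covering "Any observed cutaneous or ocular response that can be completely described by the dermatologist or ophthalmologist grading scales".

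Each of these places has one exit. In 10.1 it begins "Only in the case of unusual reactions, in the opinion of the clinical expert, will these reactions", and such reactions are then documented as AEs. Sections 8.2.3 and 8.2.4 carry a similar exit without naming who decides: "Only in the case of unusual reactions will these reactions and the consequences observed upon evaluation be documented". They govern baseline examinations before any product is used.

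On seriousness, 10.2 says: "If an event is not an AE per definition above, then it cannot be an SAE even if serious conditions are met". The expedited route in 10.3 is for SAEs: "All SAEs will be recorded and reported to the sponsor or designee immediately and under no circumstance should this exceed 24 hours". Section 10.4.2 sets the same limit for the SAE form.

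The list of events that are AEs, also in 10.1, includes safety assessments that worsen from baseline and that the investigator considers clinically significant. It also includes exacerbation of a pre-existing condition.

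**The concern.** It is reasonable not to report a scored tolerance finding a second time as an AE. The difficulty is that this rule sits inside the AE definition, and the SAE definition depends on that definition. An exemption meant to avoid double counting can therefore also switch off expedited reporting.

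Two things are at stake. The first is prompt notice to the sponsor of a serious local reaction. The second is consistent classification: local tolerance is what this study measures, and the site and the coders need one reading of when a facial or ocular reaction is an AE.

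**Working it through.** The plan gives no figure on this point, so the check sets the sections side by side.

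**1. How far the exemption reaches.** Protocol 9.2.1 has 4 skin attributes and 9.2.2 has 4 eye attributes: 4 + 4 = 8. All 8 are graded from None (0) to Severe (3), so being gradable does not mean being mild.

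**2. The exit.** 'Unusual' is left to an expert's opinion in 5.8, 8.3.1, 8.3.2 and 10.1. None of the four defines it or links it to a grade or a seriousness criterion. The tests for the exemption also differ: 5.8 requires that the scale describe the response completely, while the other three require only that the response can be graded.

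**3. The SAE chain.**
- 10.1: gradable and not unusual, so not an AE.
- 10.2: not an AE, so not an SAE, whatever its outcome.
- 10.3 and 10.4.2: the 24-hour duty attaches to SAEs.
- Result: the duty does not arise for a gradable reaction that meets a seriousness criterion and is not called unusual.

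**4. The conflict inside 10.1.** Inclusion criteria 6 and 7 (5.2) require erythema and dryness of at least 0.5, so every subject enters with both signs. Take a subject whose erythema goes from 0.5 at baseline to 3 at Visit 3, a rise of 3 − 0.5 = 2.5.

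| Entry in 10.1 | Who judges | Class |
|---|---|---|
| Safety assessment worse than baseline, clinically significant | investigator | AE |
| Exacerbation of a pre-existing condition | not stated in the entry | AE |
| Response that can be graded, not unusual | clinical expert | not an AE |

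One finding receives opposite classes, and no order of precedence is given.

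**5. Reactions away from the scheduled examinations.**
- Planned expert gradings per subject: 2 (baseline and Visit 3), with 0 in between.
- Both clinician endpoints need a score increase and a relevance call at Visit 3 (12.3.1, 12.3.2). Missing data are not imputed (12.3.8; SAP 4.4.3).
- After early withdrawal, closing expert assessments are discretionary. Section 7.2, under lost to follow-up, says they may be done and does not treat their omission as a deviation if safety was preserved. Section 8.6 allows follow-up visits with expert assessments.
- A reaction that resolves at home, or leads to withdrawal with no closing grade, is therefore not in the clinician endpoints.
- Whether it reaches the AE tables depends on how 10.1 is read. The cross-reference to 9.2 points towards responses graded by an expert at a scheduled examination. But 10.1 does not say so, and 9.2 also contains the subject self-assessment scales (9.2.3), with 5 skin and 4 eye attributes.
- Section 10.7 separates AE withdrawals by the same AE definition. On the broad reading, such a case would miss the SAP 4.6.1 listing of TEAEs leading to product discontinuation. It would still appear under the recorded reason for withdrawal (8.5; SAP 4.1.1).

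**The case against.** **The exemption is narrower than it looks.** All the passages speak of an observed response. Section 9.2 ties its assessments to the schedule of activities, and 9.2.1 and 9.2.2 tie the expert grades to the baseline and final examinations. Subjects are told to contact the site about reactions (8.2.5), diaries are reviewed for AEs (8.4), and the SAP plans Skin (Face) TEAE tables and a listing. Those displays would have little purpose if every facial reaction were exempt. This stands as evidence of intent. A reader might infer that between-visit reactions are certain to be lost from the AE tables; the documents do not support that. They leave it unsettled.

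**A serious case is remote.** Death, threat to life, hospitalization or disability is not something a 0 to 3 grade describes, and an expert would probably call such a reaction unusual. The examples in 10.2 concern the disease under study. This lowers the likelihood but leaves expedited reporting resting on an undefined opinion, and the 10.2 examples do not limit its general statement. The other notices are not substitutes: 8.5 applies at study end with no time limit, and 13.3.5 concerns new benefit/risk information, urgent safety measures and serious breaches.

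**Other stronger readings also fail.**
- Clinically relevant reactions present at Visit 3 are not lost. They are in the endpoint tables and listings (SAP 4.4.1.1, 4.5.1.1).
- The missing judge in 8.2.3 and 8.2.4 cannot hide a product reaction, because those examinations precede product use.
- One might argue that uncounted dropouts flip the 10% tolerability rule. Suppose 150/3 = 50 treated and 45 completing in an arm: 4/45 = 8.9% passes, while adding two reaction-related dropouts gives (4 + 2)/50 = 12.0%. The two dropouts are pure assumption, and the fix proposed here would not make them primary events, so this is not evidence of the size of the problem.

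**Conclusion.** The point holds as a defect in the reporting rules. Followed literally, 10.1 with 10.2 keeps a gradable reaction that meets a seriousness criterion out of the 24-hour SAE route unless it is judged unusual. Section 10.1 also contradicts itself on worsening skin findings, in a population that all enters with erythema and dryness.

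The between-visit and withdrawal point is secondary. Absence from the clinician endpoints follows from the visit schedule and the missing-data rule. Absence from the AE tables follows only on the broad reading of 10.1, which is probably not the one intended.

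No size can be given: the documents state no rate for serious, between-visit or withdrawal-causing reactions. The conclusion rests on the text alone and assumes that site staff apply it literally. It should be corrected because the safety consequence is specific and the remedy is cheap. It does not challenge the sample-size calculation or the primary endpoint.

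**What to change.** Reconcile Protocol 5.8, 8.3.1, 8.3.2, 10.1 and 10.2, and align 8.2.3 and 8.2.4 with them, so that:

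1. The exemption never overrides the seriousness criteria in 10.2. One sentence giving 10.2 priority would do this.
2. The exemption covers only responses graded by the dermatologist or ophthalmologist at a scheduled 9.2.1 or 9.2.2 assessment. Reactions reported between visits, or leading to discontinuation, are then recorded as AEs.
3. The two lists in 10.1 no longer conflict, with a stated order of precedence between worsening or exacerbation and the exemption.

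The aligned sections should use one test for the exemption and say what 'unusual' means and who judges it.

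The cost is protocol wording, a few extra AE pages and some double reporting of reactions that are also scored. Sample size and primary endpoint are unchanged.

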8.3.2 Ophthalmologist Assessment

A final assessment by the same ophthalmologist, where possible, will be completed at the end of the 21 (+2) day product use period (Visit 3).

The intensity of any visual signs of ocular irritation will be recorded according to the grade of the reactions according to the Ophthalmological Evaluation ([Ophthalmologist Assessment of Signs and Symptoms of Ocular Irritation](#)).

The ophthalmologist is responsible for grading the reactions, their opinion on the classification of the ocular irritation scores is final.

Any observed ocular response that can be denoted according to the grade of the reactions will not be considered an adverse event. Only in the case of unusual reactions, in the opinion of

the qualified ophthalmologist, will these reactions and the consequences observed upon evaluation be documented as AE's.

8.3.3 Subject self-assessment

Subjects will be asked to answer the final self-assessment questions as per section [Subject Self-Assessment of Signs and Symptoms of Cutaneous and Ocular Irritation](#) at the end of the 21 (+2) day product use period. Subject responses will be directly entered into the CRF by site staff.

8.4 Diary Review

The diary will be reviewed by the investigator, or suitably qualified designee, and the subject. Any subject comment captured in the diary which is considered an adverse event will be assessed and reported as per the defined procedure in this protocol. Adverse event reporting procedures are summarized in [Adverse Event and Serious Adverse Events](#).

Any additional comments relating to medications/treatments provided in the diary will be reviewed by the investigator or medically qualified designee with the subject and entered into the CRF as appropriate.

Additional and missed product applications will be considered deviations from the protocol and will be recorded on the Deviations Log of the CRF.

8.5 Study Conclusion

The Study Conclusion page of the CRF will be completed for all subjects whether they completed all study procedures or if they were discontinued from the study early. If the subject discontinued early, at any point during the study, the primary reason for withdrawal should be recorded on the Study Conclusion page.

If a subject has any clinically significant, study-related abnormalities or AEs at the end of the study, the GSK CH medical monitor (or designated representative) should be notified and, the subject may be asked to remain at the clinical site or be asked to return for a follow-up visit to ensure any issue is resolved or deemed not clinically significant.

8.6 Follow-up Visit

The study site may contact a subject to follow up an AE post-study completion/withdrawal and, in some circumstances, request they return to the site for additional follow-up visits (final safety (dermatologist and ophthalmologist assessments). If needed, additional examinations may be carried out at such visits.

9 STUDY ASSESSMENTS

Every effort should be made to ensure that protocol-required tests and procedures are completed as described. However, it is anticipated that from time to time there may be circumstances, outside the control of the investigator that may make it unfeasible to complete an assessment. In these cases, the investigator must take all steps necessary to ensure the safety and well-being of the subject. When a protocol-required assessment cannot be performed, the investigator (or designee) will document the reason for the missed assessment as a protocol deviation and any corrective and preventative actions that he or she has taken to

ensure that required processes are adhered to as soon as possible. The Sponsor must be informed of any missed assessments in a timely manner.

9.1 Screening Assessments

Screening assessments will be performed by appropriately trained staff/clinical examiners at the times, and in the order, defined in the [Study Procedures](#) section of this protocol

9.2 Safety and Other Assessments

The following safety assessments will be performed by appropriately trained staff/clinical examiners, at the times and in the order defined in the [Schedule of Activities](#) section of this protocol.

9.2.1 Dermatologist Assessment of Signs and Symptoms of Cutaneous Irritation

A qualified dermatologist will visually assess the signs and symptoms of cutaneous irritation. The following grades and their respective numerical equivalent scores will be used to record the response observed at the time of clinical examination at baseline (prior to product application), and the final visit.

Table 9-1 Dermatological Evaluation

Attribute	Description (Score)				
Erythema	None (0)	Very Slight (0.5)	Slight (1)	Moderate (2)	Severe (3)
Dryness	None (0)	Very Slight (0.5)	Slight (1)	Moderate (2)	Severe (3)
Scaling	None (0)	Very Slight (0.5)	Slight (1)	Moderate (2)	Severe (3)
Edema	None (0)	Very Slight (0.5)	Slight (1)	Moderate (2)	Severe (3)

For any subject who presents an increased score versus baseline, the dermatologist will further classify whether the reaction constitutes a clinically relevant positive outcome.

